APPENDIX M. PUBLICATION POLICY

All unpublished information given to the investigator by the sponsor shall not be published or disclosed to a third party without the prior written consent of the sponsor.

The results of this study may be published or presented at scientific meetings. If this is foreseen, the investigator agrees to submit all manuscripts or abstracts to the sponsor before submission. This allows the sponsor to protect proprietary information and to provide comments.

The sponsor will comply with the requirements for publication of study results:

“Recommendations for the Conduct, Reporting, Editing, and Publication of Scholarly Work in Medical Journals” (www.ICMJE.org). Publication of the results will occur in a timely manner according to applicable regulations. In accordance with standard editorial and ethical practice, the sponsor will generally support publication of multicenter studies only in their entirety and not as individual investigational center data. In this case, a coordinating investigator, if applicable, will be designated by mutual agreement.

Authorship will be determined by mutual agreement and in line with International Committee of Medical Journal Editors authorship requirements:

- substantial contributions to the conception or design of the work; or the acquisition, analysis, or interpretation of data for the work
- drafting the work or revising it critically for important intellectual content
- final approval of the version to be published
- agreement to be accountable for all aspects of the work in ensuring that questions related to the accuracy or integrity of any part of the work are appropriately investigated and resolved

The publications committee established by the sponsor will oversee this process. Additional publications may follow. Policies regarding the publication of the study results are defined in the financial agreement.

No patent applications based on the results of the study may be made by the investigator nor may assistance be given to any third party to make such an application without the written authorization of the sponsor.

APPENDIX N. MANAGEMENT OF STUDY ACTIVITIES DURING COVID-19 OUTBREAKS

This appendix addresses the modifications in study conduct during coronavirus disease 2019 (COVID-19) outbreaks.

The changes will be effective for the period of the COVID-19 outbreaks and will be implemented exclusively at the sites impacted by COVID-19. When the situation at specific sites/countries allows the return to regular study activities, the full protocol will govern the study for all sites including those who were impacted by COVID-19.

The following sections of the protocol are affected:

Section 1.3.1. Known and Potential Benefits and Risks of the Test Investigational Medicinal Product(s)

In the event of an emergency situation (eg, COVID-19 outbreaks), the sponsor, in close collaboration with the investigators, will determine if the benefit-risk assessment remains positive as a whole, and will assess any additional risks on a patient-by-patient basis. The measures outlined in this appendix are aimed at further mitigating the additional risks in an emergency situation.

It should be noted that patients diagnosed with COVID-19 will be excluded from entering run-in period and will not be randomized into the study as they would meet exclusion criterion “d”, which excludes patients with “clinical symptoms that may indicate COVID-19 infection, and/or patients who in the investigator’s opinion are at high risk of exposure to COVID-19 within 4 weeks before screening or during screening/run-in”. Such patients will be tested for active COVID-19 infection and will only be included if they test negative for COVID-19. Furthermore, exclusion criterion “c” stipulates:

- The patient has a suspected bacterial or viral infection (including COVID-19) of the upper or lower respiratory tract, sinus, or middle ear that has not resolved at least 2 weeks before the screening period. Note: Patients who develop an upper respiratory infection/lower respiratory infection (URI/LRI) during the run-in period may rescreen 2 weeks after symptoms resolve and undergo COVID-19 testing as outlined in exclusion criteria “d”.

Older adults and people of any age who have serious underlying medical conditions, including moderate to severe asthma, may be at higher risk for a more severe COVID-19 course when infected ([Centers for Disease Control and Prevention \[CDC\] Coronavirus \[COVID-19\]](#)).

The protocol also states that if a patient exhibits clinical symptoms that may indicate COVID-19 infection after entering the study, he/she should be tested for active COVID-19. If the patient tests positive for active COVID-19 (positive antigen testing must be confirmed by reverse transcription polymerase chain reaction [RT-PCR]), he/she may continue for scheduled visits when recovered (ie, 10 days after onset of symptoms, is afebrile for 24 hours without use of anti-pyretics and demonstrates improvement in other symptoms), assuming he/she has no protocol violations including use of disallowed medications (see Section 4.4).

Section 3.1. General Study Design and Study Schematic Diagram; Section 3.5. Schedule of Study Procedures and Assessments; Appendix B. Study Procedures and Assessments by Visit

In the event of an emergency situation (eg, COVID-19 outbreaks), in case a patient cannot return to the clinic for the scheduled visits (eg, due to quarantine, isolation, patient's concern, active COVID-19 infection, or closure of the site clinic), the patient will continue with daily hand-held spirometry measurements and e-diary completion, and scheduled adverse event and concomitant medication monitoring. Patient questionnaires may be completed with the assistance of study center personnel where permitted by licensing agreements. If the patient tests positive for active COVID-19, he/she may continue for scheduled visits when recovered, as specified above, assuming he/she has no protocol violations including use of disallowed medications (see Section 4.4). Where appropriate, remote assessment of safety via telephone and/or videoconference (VC), with VC being the preferred method, is recommended until the patient attends his/her next scheduled visit. All other tests (including safety laboratory tests, pharmacokinetics, ADA, and biomarkers) are to be conducted once the patient can return to the study center for his/her next scheduled visit unless collected at a local laboratory or home nurse visit depending on availability and local regulation. Samples from patients with known active COVID-19 infection should not be collected.

In the event that a patient completes the run-in but cannot come to the site for the day of randomization (DoR) visit for randomization (eg, due to quarantine, isolation, patient's concern, or closure of the site clinic), it may be possible to extend the duration of run-in on a case-by-case basis, following discussion between the investigator and the sponsor study physician. Rescreening of the patient will also be allowed.

Modifications to other procedures and assessments (electrocardiogram [ECG], laboratory sample collection, pharmacokinetic sampling, etc.) will be performed per implemented contingency measures according to sponsor instructions and the corresponding manual. For example, if central laboratory samples cannot be collected for safety assessments, sites may have patients visit a local reference laboratory or dispatch a home health nurse to perform the assessments, but only after consultation with the sponsor and as allowed by local regulation.

These measures will be implemented on a case-by-case basis, and only when and where they are warranted due to the emergency situation. Preferably, the original protocol instructions will be followed whenever the modified instructions are not required.

Section 4.2 Patient Exclusion Criteria; Section 4.3. Randomization Criteria; Section 5.7. Prior and Concomitant Medication or Therapy

In the event that new COVID-19 therapies or vaccines become available during the study, the eligibility criteria and list of prohibited medications can be updated to reflect these developments. If a patient receives new COVID-19 therapies not in compliance with the eligibility criteria and list of prohibited medications current at the time of the patient's participation in the study, the investigator and sponsor will discuss how to proceed on a case-by-case basis.

Section 4.4. Withdrawal Criteria and Procedures for the Patient

If a patient exhibits clinical symptoms that may indicate COVID-19 infection after entering the study, the patient should be tested for active COVID-19. If the patient tests positive for active COVID-19 (confirmed by RT-PCR), he/she may continue for scheduled visits when recovered, as specified above, assuming he/she has no protocol violations including use of disallowed medications ([Appendix G](#)).

Where appropriate, remote assessment of safety via telephone and/or VC, with VC being the preferred method, is recommended until the patient attends his/her next scheduled visit. All other tests (including safety laboratory tests, pharmacokinetics, ADA, and biomarkers) are to be conducted once the patient can return to the study center for his/her next scheduled visit.

Section 4.5 Replacement of Patients

In the event of an emergency situation (eg, COVID-19 outbreaks), if the proportion of patients who terminate the study early due to reasons other than loss of asthma control exceeds the anticipated 15%, the number of patients to be randomized may be increased to ensure the targeted number of completers per arm.

Section 6. Assessment of Efficacy

In the event of an emergency situation (eg, COVID-19 outbreaks), if a patient cannot return to the clinic for the scheduled visits (eg, due to quarantine, isolation, patient's concern, active COVID-19 infection, or closure of the site clinic), remote assessment of efficacy via telephone call and/or VC, with VC being the preferred method, may be allowed. Uploaded electronic diary data for rescue medication usage, daytime and night-time asthma symptom scores, and uploaded hand-held spirometry data will be reviewed remotely. Telephone/VC assessment by the investigator will be assessed at the scheduled visit. Clinic-based forced expiratory volume in 1 second (FEV₁) assessments will not be possible unless a satisfactory home spirometry device that is generally equivalent can be implemented. The results of the clinical asthma exacerbation (CAE) inquiry will be entered directly into the CRF per the usual process. Questionnaire data will be completed and entered into the CRF per the usual process or will be collected by validated paper questionnaire and entered into the database by the study personnel.

Preferably, the original protocol instructions will be followed whenever the new instructions are not required.

These measures will be implemented on a case-by-case basis, and only when and where they are warranted due to the emergency situation. Preferably, the original protocol instructions will be followed whenever the modified instructions are not required.

Section 7. Assessment of Safety

In the event of an emergency situation (eg, COVID-19 outbreaks), if a patient cannot return to the clinic for the scheduled visits (eg, due to quarantine, isolation, patient's concern, active COVID-19 infection, or closure of the site clinic), remote assessment of safety (as well as inquiries regarding adverse events and use of concomitant medication) via telephone call and/or VC, with VC being the preferred method, may be allowed. The results will be directly entered into the CRF per the usual process.

Modifications to other procedures and assessments (ECG, laboratory sample collection, pharmacokinetic sampling, etc.) will be performed per implemented contingency measures according to sponsor instructions and the corresponding study reference manual. For example, if central laboratory samples cannot be collected for safety assessments, sites may have patients visit a local reference laboratory or dispatch a home health nurse to perform the assessments, but only after consultation with the sponsor and as allowed by local regulation.

These measures will be implemented on a case-by-case basis, and only when and where they are warranted due to the emergency situation. Preferably, the original protocol instructions will be followed whenever the modified instructions are not required.

Active COVID-19 cases will be monitored throughout the study. If a total number of COVID-19 infections are confirmed in randomized patients who received IMP (placebo or TEV-53275) and related to an SAE to reach a minimum threshold (based on total randomized patients, detailed in the medical monitoring plan), the Pharmacovigilance physician in consultation with the Clinical Study Physician will determine if an unblinded review of the cases is warranted to ensure patient safety. Any unblinded review will be conducted by appropriate personnel that are not connected with the study.

Section 7.4. Clinical Laboratory Tests

If central laboratory samples cannot be collected for safety assessments, sites may have patients visit a local reference laboratory or arrange a home health visit to perform the assessments after discussion with and approval by the sponsor and as allowed by local regulation.

Section 7.4.2.4. COVID-19 Testing

Testing of patients asymptomatic for COVID-19 active infection may be conducted at the discretion of the investigator within 72 hours of any visit where spirometry assessments are to be conducted or as required by health authorities, local ethics committees, or study center standard operating procedures (SOPs). The testing may be conducted by the central laboratory or locally depending on feasibility. Positive tests that measure COVID-19 antigen must be confirmed by RT-PCR.

Section 7.5. Physical Examinations; Section 7.6. Vital Signs; Section 7.7. Electrocardiography; Section 7.8. Assessment of Local Tolerability and Pain

After consultation with the sponsor and as allowed by local regulation, at home health visits may be used to perform safety assessments such as physical examinations, vital signs, ECG, and local tolerability, and nursing assessments to determine any new adverse events. The patient will continue with daily hand-held spirometry measurements and e-diary completion during this time.

Section 8. Assessments of Pharmacokinetics, Immunogenicity, Biomarkers, and Pharmacogenetics

If pharmacokinetic, immunogenicity, and/or biomarker samples cannot be collected due to limitations in the ability to carry out the procedure or limitations in storage and shipments, the samples will not be collected for those respective visits. Study samples collected from confirmed COVID-19 positive patients during the study, with confirmation either before or after the sample collection, will be kept at the central laboratory and will not be shipped to Teva bioanalytical laboratories nor analyzed. Teva bioanalytical laboratories will be informed by the sponsor within

approximately 1 week of any patients confirmed COVID-19 positive after samples have been collected.

Section 9. Statistics

Sensitivity and supplementary analyses may be conducted to evaluate the impact of the change to remote monitoring (telephone calls and VC visits) and the impact of COVID-19 outbreaks on study endpoints, eg, as follows:

1. A sensitivity analysis which will include eligible home-based efficacy assessment values for those who cannot be remotely evaluated due to outbreak emergency situations.
2. A sensitivity analysis which will treat the efficacy assessment values collected through remote evaluation as missing and apply the usual missing data handling approach (reference-based multiple imputation).

In addition, the amount of home-based efficacy assessments and missing data due to the outbreak will be monitored continuously and the sample size will be re-assessed to ensure sufficient study power.

Details of the supplementary and sensitivity analyses will be presented in the statistical analysis plan or addendum thereof, following a blinded review meeting prior to database lock.

Section 10. Quality Control and Quality Assurance

Deviations from the study conduct due to emergency situations (eg, COVID-19 outbreaks), including implemented contingency measures and their impact (eg, patient discontinuation from the study, alternative procedures used to collect critical safety and/or efficacy data, etc.), will be described in the appropriate sections of the clinical study report (CSR) as applicable.

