
A secondary objective of the study is to evaluate the safety and tolerability of TEV-53275 administered sc in adult patients with persistent asthma and an eosinophilic phenotype compared with placebo
	
The secondary safety and tolerability endpoints are:
 
 frequency of adverse events changes from baseline in clinical laboratory test results (serum chemistry, hematology, and urinalysis) throughout the study changes from baseline in vital signs (blood pressure, pulse rate, respiratory rate, and body temperature) throughout the study changes from baseline in 12-lead electrocardiogram (ECG) findings throughout the study use of concomitant medication local tolerability number (%) of patients who did not complete the study due to adverse events

A secondary objective of the study is to evaluate the immunogenicity of TEV-53275 administered sc in adult patients with persistent asthma and an eosinophilic phenotype
	
The immunogenicity will be assessed by measuring the development anti-drug antibodies (ADA), and the titer and neutralizing activity of the ADA at baseline and throughout the study

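### Read literally, Appendix N leaves unanalysed every PK, ADA and IL-5 sample still held from a patient confirmed COVID-19 positive during the study, with no window around the infection and no release after recovery.

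*Protocol*

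**What the plan says.** The hold appears in Protocol Appendix N under the heading "Section 8. Assessments of Pharmacokinetics, Immunogenicity, Biomarkers, and Pharmacogenetics". It applies to study samples from patients confirmed COVID-19 positive during the study. Such samples, "with confirmation either before or after the sample collection, will be kept at the central laboratory and will not be shipped" to the sponsor's bioanalytical laboratories, nor will they be analysed. The only time given there concerns notification: the sponsor is to inform the bioanalytical laboratories within "approximately 1 week of any patients confirmed COVID-19 positive after samples have been collected".

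Elsewhere in Appendix N, the text on Sections 3.1 and 3.5 and on Appendix B lets a patient who tested positive resume scheduled visits after recovery. It adds that "All other tests (including safety laboratory tests, pharmacokinetics, ADA, and biomarkers) are to be conducted once the patient can return to the study center", with allowance for local or home collection, and sets one limit on collection: "Samples from patients with known active COVID-19 infection should not be collected". The Appendix N text on Section 4.4 repeats the instruction to sample on return.

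Immunogenicity is a secondary objective. Protocol Section 2.1 assesses it by the development of ADA and "the titer and neutralizing activity of the ADA at baseline and throughout the study".

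**The concern.** A hold on blood drawn around an infection is easy to understand. This one also covers a Day 0 sample from a patient infected months later and a week 30 sample from a patient who recovered months earlier. Neither is a sample that the collection rule in the same appendix would stop.

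Three features of the plan make the loss matter:

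- A completer gives only three routine ADA samples (V3, V9 and V10). Protocol Section 3.3 relies on the follow-up visit to detect ADA when drug levels are low or undetectable. The hold can remove all three. It also makes no exception for the event-driven ADA samples requested in Section 8.3.
- The PK analysis set (Section 9.2.5) requires at least one available concentration, so a patient with none analysed drops out. The ADA analysis set (Section 9.2.6; SAP Section 3.6) has no such requirement, so a patient without any ADA result can stay in the denominator.
- The plan treats FEV1 more narrowly. SAP Section 1.3.1 removes only observations after diagnosis, and only for moderate or severe COVID-19 or a COVID-related serious adverse event. A patient with a mild infection keeps all FEV1 data in that estimand but could lose every bioanalytical result.

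**Working it through.** The plan states no figure on this point, so there is none to reproduce. The check compares the texts and then sizes the loss under stated assumptions.

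**1. Is there a time limit?** The hold gives no number of days before or after confirmation and no release on recovery. The week mentioned is a notification time. The opening of Appendix N limits its measures to outbreak periods and affected sites, which sets no limit relative to a patient's own infection.

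**2. Do the hold and the collection rule agree?**

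| Time of draw | Collection | Analysis under the hold |
|---|---|---|
| Before infection | Yes (Table 2, Appendix B) | Barred if still held |
| Known active infection | No (Appendix N) | No sample should exist |
| After recovery | Yes (Appendix N) | Barred |

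The last row is the direct conflict. The first row is a consequence of the missing window.

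**3. Scheduled samples per patient (Table 2, Appendix B).** PK and IL-5 are drawn on days 0, 3, 14, 28, 56, 84, 112 and 210, so 8 each. ADA is drawn on days 0, 112 and 210, so 3.

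**4. Two example patients, assuming nothing was shipped before confirmation.** Section 4.4 counts a patient as recovered after 10 days from symptom onset, if fever and other symptoms allow. I take onset and confirmation on the same day and recovery at 10 days, before any safety margin.

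- *Onset at week 20 (day 140).* There are 7 PK/IL-5 visits before and 1 after: 7 + 1 = 8 held. ADA: 2 + 1 = 3 held. A window from day 140 to day 150 contains no scheduled clinic visit, so a windowed hold would cost 0.
- *Onset at week 3 (day 21).* There are 3 visits before (days 0, 3, 14). Day 28 falls 28 − 21 = 7 days after onset, so no sample is taken then. There are 4 visits after (days 56, 84, 112, 210). PK/IL-5: 3 + 4 = 7 held. ADA: 1 + 2 = 3 held. A window from day 21 to day 31 affects only the day 28 visit.

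The first gaps are 3 days and 11 days, so an early infection or slow recovery could cost more than one visit even with a window.

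**5. Upper bound across the trial.** About 300 patients at 1:1:1 give 300 × 2/3 = 200 on TEV-53275. The infection rate r over the 30 weeks is an assumption.

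| r | Patients with no result (200 × r) | ADA samples (× 3) | PK samples (× 8) |
|---|---|---|---|
| 5% | 10 | 30 | 80 |
| 10% | 20 | 60 | 160 |
| 20% | 40 | 120 | 320 |

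**6. Effect on ADA incidence if untested patients stay in the denominator.** With true incidence p the same in infected and uninfected patients, the apparent incidence is p × (1 − r). For an assumed p = 5%: 0.05 × 0.95 = 4.75%, 0.05 × 0.90 = 4.5%, 0.05 × 0.80 = 4.0%.

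**The case against.** The strongest reply is that the sentence has a narrower meaning. It may be aimed at samples drawn while the patient was infected, whether the confirming result came before or after the draw. Antigen positives need RT-PCR confirmation, and asymptomatic testing may fall within 72 hours of a visit, so late confirmation is a real situation. On that reading the sections would not conflict. It explains confirmation after the draw well, but confirmation before the draw poorly: once infection is confirmed and active, samples should not be collected, so the samples reached are mainly post-recovery ones. At best the sentence is ambiguous, and a laboratory following its words would hold too much. A biosafety reason is plausible but not stated, and would not explain an open-ended hold.

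Other parts of the reply stand, and they rule out stronger readings that a reader might infer:

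- *That the samples are discarded.* They are retained at the central laboratory, so a clarified rule could still release them.
- *That any past infection triggers the hold.* The wording is tied to confirmation during the study and does not clearly reach an infection before enrolment.
- *That every sample from an infected patient is certainly lost.* Samples already shipped cannot be kept back. Protocol Section 5.10.2 allows PK and immunogenicity data to be assessed during the study, and shipping details are in the study reference manual, which is not available here.
- *That key efficacy results are at risk.* PK and IL-5 summaries are descriptive, and the effect of ADA is evaluated only where appropriate. Blood eosinophils come from central-laboratory blood counts, so a bar on shipment to the sponsor's laboratories does not remove them.

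SAP Section 12 places immunogenicity outside its scope. Some neighbouring SAP text is blacked out, so a handling rule there cannot be excluded.

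**Conclusion.** The point holds as a conflict within Appendix N and a missing window. Followed as written, the hold leaves usable PK, ADA and IL-5 samples unanalysed for patients confirmed positive during the study, including post-recovery samples that the appendix itself directs sites to take.

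The consequence is limited to the secondary immunogenicity objective and the descriptive PK and IL-5 results; the primary FEV1 analysis is untouched. The 10, 20 or 40 patients are upper bounds. They rest on assumed infection rates, the planned 300 randomised patients, a literal reading of the hold, and no affected sample having been shipped or analysed before confirmation. The true loss cannot be determined from the documents. The correction is worth making because it is cheap and recovers data from blood that patients have already given.

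**What to change.** Reword the Appendix N text on Section 8 so that the hold covers only samples drawn in a stated window:

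- **Start:** a safety margin set by the laboratory, before symptom onset or the first positive test, whichever is earlier.
- **End:** when the Section 4.4 recovery definition is met. That definition counts from symptom onset, so for asymptomatic positives give a stated interval counted from the positive test.
- **Outside the window:** ship and analyse retained samples as usual.
- **Notice to the bioanalytical laboratory:** give the window dates as well as the patient.
- **Samples already shipped or analysed before confirmation:** state how they and their results are handled.
- **ADA reporting:** calculate incidence among patients with an evaluable ADA result, and show how many treated patients have none.

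The cost is a short rewording of Appendix N, a matching line in the laboratory instructions, a reporting rule for ADA, and the assay of samples already in storage. No extra visits or blood draws are needed.
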